In this randomized, cross-over study 20 subjects who are undergoing testosterone (T) therapy for the treatment of T deficiency will receive both subcutaneous testosterone therapy and intramuscular testosterone therapy. One group will receive a SQ injection followed by an IM injection and one group will receive an IM injection followed by a SQ injection. The primary objective of this study is to measure testosterone concentration in men after these two treatment routes and determine if there are any significant differences due to modes of administration. Endpoints will include total serum testosterone and calculated free testosterone. A questionnaire will also be administered to assess overall patient experience with each route of administration.

Schedule of activities

	Pre-Enrollment (prior to Day 0)	Visit 1 Day 0	Visit 2 Day 3	Visit 3 Day 7	Visit 4 Day 14	Visit 5 Day 17	Visit 6 Day 21	End of Study Day 28
Window	-14 to 0 days	± 0 days	± 2 days	± 2 days	± 2 days	± 2 days	± 2 days	± 2 days
Informed consent	X							
Eligibility assessment ¹ • Laboratory testing ²	SC							
Questionnaires ³	SC	X			X			X
Testosterone Treatment • Pain rating ⁴		SC			SC			
Blood sampling • Beckman Coulter ⁵		X	X	X	X	X	X	X
End of study ⁶								

¹ Eligibility labs: use the most recent values performed as part of routine clinical care: [1] total testosterone, [2] free testosterone, [3] PSA

² Other lab data collected: use the most recent values performed as part of routine clinical care: [1] estradiol, [2] LH, [3] FSH, [4] SHBG, [5] hematocrit

³ Responses collected for: [1] Low Testosterone Questionnaire | © 2014 Men's Health Boston, [2] International Prostate Symptom Score (IPSS) | American Urological Association

⁴ Rating pain after injection on Likert scale

⁵ Samples collected for: visits 1, 4, 7: [1] total testosterone, [2] free testosterone, [3] PSA; visits 2, 3, 5, 6: [1] total testosterone, [2] free testosterone, [3] estradiol, [4] LH, [5] FSH, [6] SHBG, [7] hematocrit, [8] PSA

⁶ End of study survey – preferred mode of administration

X = Research only

SC = Standard care

Table of contents

List of abbreviations and definitions	7
1. Introduction	8
1.1 Background	8
1.2 Rationale and hypothesis.....	8
2. Objectives	8
2.1 Primary outcome and endpoint.....	8
2.2 Secondary outcomes and endpoints.....	8
3. Study design	9
4. Study population	9
4.1 Inclusion criteria	9
4.2 Exclusion criteria.....	9
4.3 Protected populations	9
5. Trial interventions	10

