T deficiency is often treated with testosterone therapy of which various delivery methods are available³. Treatment is aimed at inducing and maintaining secondary sex characteristics and improving sexual function, sense of well-being, and bone mineral density⁴. Although testosterone was first synthesized in 1935, treatment options are continually evolving⁵.

One standard treatment for TD is intramuscular (IM) injections of exogenous T⁶. However, subcutaneous (SQ) injections may have some advantages compared to IM injections. SQ injections is more convenient and less challenging than IM for men who are candidates for self-injection. SQ also involves a smaller needle and may be less intimidating to patients. This trial will investigate how serum testosterone levels are affected by the route of T administration.

1.2. **Rationale and hypothesis**

The purpose of this study is to preliminarily determine if the route of delivery of testosterone therapy affects testosterone concentrations in men. Our hypothesis that SQ will provide comparable or acceptable T concentrations as IM, with regard to duration of action and peak or average concentrations.

2. Objectives

2.1. **Primary outcome and endpoint (endpoint bulleted below)**

The primary objective of this study is to determine how testosterone concentration in men differs based on administration route for T injections in men.

The Primary endpoints are total testosterone concentration and calculated free T concentration following injection, measured by Beckman assays and equipment.

2.2. **Secondary outcomes and endpoints (endpoints bulleted below)**

The Secondary endpoints are responses to Low Testosterone Questionnaire, International Prostate Symptom Scores, and levels of estradiol, LH, FSH, SHBG, and PSA following injection, measured by Beckman assays and equipment and hematocrit following injection measured by Quest Diagnostics.

3. Study design

In this single-center clinical trial, 20 subjects being treated with testosterone therapy for T deficiency will be randomized to subcutaneous testosterone injection followed by intramuscular testosterone injection or intramuscular testosterone injection followed by subcutaneous testosterone injection. Subjects will be screened for eligibility and subsequently randomized at the baseline visit, then followed for four weeks.

4. Study population

4.1. **Inclusion criteria**

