6.3. Recruitment and consent

A member of the study staff will explain study procedures in detail to the potential subject. The study staff member will clearly outline that the purpose of the study is to compare the testosterone concentrations following two different routes of testosterone therapy. While any study staff member may conduct the informed consent discussion and obtain informed consent, a study physician will be available at all times for any consent-related questions. Undue coercion will be prevented by stressing that participation in this study is voluntary and the future care of the potential subject will not be affected by his decision regarding participation in this study.

7. Activities and measurements

Subjects planning to initiate testosterone treatment via injection at MHB will be consented into the study. Upon enrollment in the study, the randomization will be completed for each subject.

Blood collection will occur before each injection. Subjects will rate pain on the Likert scale following each injection. After treatment with the first mode of T administration (SQ or IM depending on randomization), subjects will come in for blood draws 3 days and 7 days following the injection. Two weeks after the initial injection, subjects will come in for treatment with the second mode of T administration (SQ or IM depending on randomization). Subjects will come in for blood draws 3 days and 7 days following the second injection. Two weeks after the second injection, subjects will complete an end of study assessment with an Investigator and will complete a survey assessing their satisfaction with treatment. Subjects will likely continue testosterone therapy at Men's Health Boston after completion of the study.

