7.2. Blood sample collection

At each visit, up to 14mL (approximately 3 teaspoons) of blood will be collected for study purposes. The serum samples (approximately 6mL) will be frozen and shipped to Beckman Coulter for analysis. Whole blood samples (approximately 3mL) will be sent to Quest Diagnostics for analysis.

	At each visit	Total for study
Total amount collected for study	13mL (4 teaspoons)	91mL
Amount of serum shipped to Beckman	6mL	42mL
Amount of whole blood for Quest	4mL	28mL

The Investigator will review all laboratory test results. Laboratory test results that are considered clinically significant by the Investigator will be followed to satisfactory resolution. Laboratory abnormalities are considered to be adverse events only if they result in discontinuation from the study, necessitate therapeutic medical intervention, and/or if the Investigator considers them to be an adverse event.

Beckman Coulter will arrange for samples to be tested for this study. Contact information is listed below:

Name:	[name] Staff Clinical Studies Scientist Beckman Coulter, Inc.
Address:	Immunoassay Business Center [name]
[contact]
Email:	[contact]

Quest will analyze whole blood samples for this study. Contact information is listed below:

Name:	Quest Diagnostics
Address:	[name]
[contact]

Sample collection

Seven blood samples will be obtained throughout the study. Samples will be collected at the following visits:

- Visit 1
- Visit 2
- Visit 3
- Visit 4
- Visit 5
- Visit 6
- End of Study

Sample processing and storage

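### Estradiol, LH and FSH are not measured in the study assay before either injection or 14 days after it, which weakens (but does not remove) the route comparison on these secondary endpoints

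*Combined protocol and SAP*

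**What the plan says.** Section 2.2 lists among the secondary endpoints "levels of estradiol, LH, FSH, SHBG, and PSA following injection, measured by Beckman assays and equipment".

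Footnote 5 to the schedule of activities splits the visits into two panels. For Days 0, 14 and 28 it gives "Samples collected for: visits 1, 4, 7: [1] total testosterone, [2] free testosterone, [3] PSA". For Days 3, 7, 17 and 21 it gives "visits 2, 3, 5, 6: [1] total testosterone, [2] free testosterone, [3] estradiol, [4] LH, [5] FSH, [6] SHBG, [7] hematocrit, [8] PSA". Section 7.1 repeats the same split, so this is the intended schedule and not a slip in one table.

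Section 7 fixes the timing: "Blood collection will occur before each injection", and "Two weeks after the initial injection, subjects will come in for treatment with the second mode of T administration". Visits 1 and 4 are therefore the pre-injection draws, and Visit 4 and End of Study are the 14-day draws.

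The one earlier source for these hormones is footnote 2: "use the most recent values performed as part of routine clinical care: [1] estradiol, [2] LH, [3] FSH, [4] SHBG, [5] hematocrit". It names no assay and sets no explicit limit on the age of the result.

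The table in section 7.2 has a row headed "Amount of serum shipped to Beckman", showing 6 mL at each visit and 42 mL in total. Section 8.2 names no model and no baseline, period or carry-over term.

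**The concern.** Under section 4 the men are about to start testosterone, and anyone previously exposed must have been off it for at least 12 weeks. Period 1 therefore begins untreated, while period 2 begins 14 days after a testosterone injection. If the first injection still affects estradiol, LH or FSH at Day 14, the values at Days 17 and 21 carry some of that effect along with the second route's own effect. The draw that would show where period 2 starts is taken, but these hormones are not run on it.

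Two further things are lost. There is no untreated baseline in the same assay as the endpoint values. There is also no estradiol, LH or FSH value at the end of either dosing interval, so the study cannot say whether the routes differ on these hormones by then.

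**Working it through.** **The plan's own figure.** Section 8.1 states 80% power with 20 subjects, two-sided 0.05, for 0.663 SD per SD. Treated as a regression slope with 18 df, the detectable slope is (t[0.975] + t[0.80])/√20 = (2.101 + 0.862)/4.472 = 0.6625. Noncentral-t power at 0.663 is 80.1%. The figure reproduces, and this point does not rest on it.

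**Count of values per hormone** (20 men, section 8.1; visits from footnote 5 and section 7.1).
- Draws: 20 × 7 = 140. With the hormone: 20 × 4 = 80 (57%). Without: 20 × 3 = 60.
- Pre-injection values: 20 × 2 = 40 possible (Visits 1 and 4), 0 obtained.
- 14-day values: 20 × 2 = 40 possible (Visit 4 and End of Study), 0 obtained. Visit 4 counts in both lists, so the distinct missing samples number 60.

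**What carry-over does to the route contrast.** Let τ be the SQ minus IM effect, π the period effect, and λ_SQ and λ_IM the first-route effects still present at the period-2 measurement days (17 and 21).
- SQ then IM: period 1 = τ; period 2 = π + λ_SQ; difference = τ − π − λ_SQ.
- IM then SQ: period 1 = 0; period 2 = τ + π + λ_IM; difference = −τ − π − λ_IM.
- Half the difference between sequences: τ + (λ_IM − λ_SQ)/2.

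Equal carry-over cancels. Unequal carry-over biases the contrast by half the inequality. For illustration, λ_SQ = −0.5 SD and λ_IM = −1.0 SD give (−1.0 + 0.5)/2 = −0.25 SD.

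**How well the existing data could cope** (assuming 10 men per sequence).
- Period 1 only, Days 3 and 7: no carry-over. Detectable difference at 80% power = (2.101 + 0.862) × √(1/10 + 1/10) = 2.963 × 0.447 = 1.33 SD.
- Between-sequence test of subject totals for unequal carry-over: standard error = √(2(1 + ρ)) × √0.2 SD, where ρ is the within-subject correlation, which the documents do not give.

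| ρ (assumed) | Power at 0.5 SD | Power at 1.0 SD |
|---|---|---|
| 0.3 | 10.1% | 25.9% |
| 0.5 | 9.4% | 23.1% |
| 0.7 | 8.9% | 21.0% |

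**What subtracting Visit 4 would do.** Write c = λ_IM − λ_SQ at Days 17 and 21, and L for the same difference at Day 14. Analysing change from Visit 1 in period 1 and from Visit 4 in period 2 turns the bias from c/2 into (c − L)/2. If c = 0 and L = −0.5 SD, an unbiased contrast acquires a bias of (0 + 0.5)/2 = 0.25 SD.

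**The case against.** A reader might infer that, without a Visit 4 value, the second route's effect cannot be separated from the first's at all. The documents do not support that. The randomised period-1 comparison is untouched by carry-over, equal carry-over drops out of the within-subject contrast, and unequal carry-over can be estimated from between-sequence totals. Those routes are imprecise, but they exist.

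Other tempting readings also go too far:
- That the bias is half the Day 14 difference between routes. It is half the difference still present at Days 17 and 21, after the second injection, and nothing in the documents makes the two equal.
- That section 1.2's interest in duration of action calls for 14-day hormone values. That hypothesis concerns testosterone, which is measured at Days 14 and 28.
- That the plan will subtract a routine-laboratory value from a Beckman value. Section 2.2 speaks of levels after injection, and neither it nor section 8.2 defines a change from baseline.
- That the routine-care values may be of any age. The pre-enrollment column carries a −14 to 0 day window, although footnote 2 asks only for the most recent result.

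It is also fair to say that these are secondary endpoints in a study that calls itself preliminary, and that both primary endpoints are scheduled at all seven visits. This limits the weight of the point. It does not supply the missing measurements, for which the serum is already being shipped.

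**Conclusion.** The gap is real and cheap to close. For each of estradiol, LH and FSH, 60 of 140 draws yield no value, and they are exactly the pre-injection and 14-day draws. As a result, any residual first-route effect at the start of period 2 is unseen, there is no same-assay untreated baseline, and no end-of-interval route comparison is possible on these hormones. The Day 3 and Day 7 against Day 17 and Day 21 comparison remains usable but exposed: bias of half any unequal carry-over, about 9–10% power to detect an inequality of 0.5 SD, and a carry-over-free fallback that detects only about 1.33 SD.

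This rests on equal allocation to the two sequences, an assumed within-subject correlation of 0.3 to 0.7, and section 4's description of men starting treatment (the opening summary and section 3 describe men already on it). The documents give no size for suppression at Day 14, so the bias figures are illustrations. The 12-week off-therapy criterion, set beside the 14-day gap, makes residual effect worth measuring but does not show that it occurs.

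**What to change.** In footnote 5 and section 7.1, add estradiol, LH and FSH at Visits 1, 4 and End of Study, run on the serum already sent to Beckman. Add SHBG too, since it has the same gap; if it enters the free testosterone calculation, which the documents do not specify, it is also needed at those visits for a primary endpoint.

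In section 8.2, state how the new values will be used:
- Visit 1, not the routine-care result, is the untreated baseline, for example as a covariate in the period-1 comparison.
- Day 14 against Day 28 is the end-of-interval route comparison.
- Visit 4 is reported by sequence to show residual first-route effect. It enters only a sensitivity analysis and is not subtracted as a period baseline, because it is measured after randomisation and affected by the first route. It shows carry-over but does not by itself remove it.

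Cost: three further assays (four with SHBG) on up to 60 samples, that is 180 (240) determinations. Section 11.8 has the sponsor paying for study laboratory testing. The same 6 mL already has to serve the longer panel at Visits 2, 3, 5 and 6, so no extra blood, visits or staff appear necessary. The sample size and the power statement are unchanged.

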7.1. Data to be recorded

Pre-enrollment

- Low Testosterone Questionnaire
- International Prostate Symptom Score
- Total Testosterone
- Calculated free Testosterone
- Estradiol
- LH
- FSH
- SHBG
- Hematocrit
- PSA

Visits 1 and 4

- Concomitant medication review and adverse event assessment
- Low Testosterone Questionnaire
- International Prostate Symptom Score
- Total Testosterone
- Calculated Free Testosterone
- PSA
- Pain rating following injection

Visits 2, 3, 5, and 6

- Concomitant medication review and adverse event assessment
- Total Testosterone
- Calculated Free Testosterone
- Estradiol
- LH
- FSH
- SHBG
- Hematocrit
- PSA

End of Study

- Concomitant medication review and adverse event assessment
- Low Testosterone Questionnaire
- International Prostate Symptom Score
- Total Testosterone
- Calculated free Testosterone
- PSA
- Survey

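### Calculated free T is a primary endpoint at every visit, but no SHBG is listed at Day 14 or Day 28, the last sample for each route

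*Combined protocol and SAP*

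**What the plan says.** Section 2.1 states: "The Primary endpoints are total testosterone concentration and calculated free T concentration following injection". The hypothesis in Section 1.2 is that the subcutaneous route compares acceptably with the intramuscular route "with regard to duration of action and peak or average concentrations".

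The analytes are listed in two places, and the two agree.

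- **Schedule of activities, footnote 5.** The visits fall into two groups: "visits 1, 4, 7: [1] total testosterone, [2] free testosterone, [3] PSA; visits 2, 3, 5, 6". The first group (Visit 7 being End of Study) has total T, free T and PSA only. The second group adds estradiol, LH, FSH, SHBG and hematocrit.
- **Section 7.1.** "Calculated free Testosterone" is an item at pre-enrollment and at all seven visits. SHBG appears at pre-enrollment, where footnote 2 takes the latest routine-care value, and at Visits 2, 3, 5 and 6.

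On timing, Section 7 says "Blood collection will occur before each injection" and "Subjects will come in for blood draws 3 days and 7 days following the second injection", with the end-of-study visit two weeks after the second injection. On samples, Section 7.2 says "The serum samples (approximately 6mL) will be frozen and shipped to Beckman Coulter for analysis", and its volume table counts this serum at every visit.

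No section gives a formula or an albumin value for free T, or says which SHBG to use at a visit where none is listed.

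**The concern.** A calculated free T is normally derived from total T and SHBG, often with albumin, all from the same blood sample. The plan requires the result at seven visits but lists this input at four. Two of the three visits without it are the final sample of each treatment period.

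Those two samples, 14 days after each injection, are the latest observations on each route and bear most on duration of action. If the listed panels are run and nothing more, free T at those times is either missing or computed with an SHBG from another day. No rule is given, so that choice would be made after the data are in hand. The plan itself treats SHBG as worth following after injection, since it is a secondary endpoint measured four times.

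Visit 1 also lacks SHBG, but the endpoint is defined after injection, so this matters only if a free T baseline is wanted.

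**Working it through.** **1. Samples with and without a listed SHBG** (footnote 5, Section 7.1, and the timing in Section 7)

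| Visit | Day | Route in effect | Free T listed | SHBG listed |
|---|---|---|---|---|
| 1 | 0 | none (before first injection) | yes | no |
| 2 | 3 | first | yes | yes |
| 3 | 7 | first | yes | yes |
| 4 | 14 | first (before second injection) | yes | **no** |
| 5 | 17 | second | yes | yes |
| 6 | 21 | second | yes | yes |
| End of Study | 28 | second | yes | **no** |

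Post-injection samples per man: 6. Without SHBG: 2, so 2/6 = 33%, or one of the three times on each route. For 20 completers this is 20 × 2 = 40 of 20 × 6 = 120. Day 28 alone accounts for 20.

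**2. What could be substituted**

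- Day 14: the earlier value is from Day 7, 14 − 7 = 7 days before. With the ±2-day windows the gap runs from 12 − 9 = 3 to 16 − 5 = 11 days. The later value, Day 17, is 3 days away by schedule but follows the injection by the other route.
- Day 28: the only choice after the second injection and near in time is Day 21, with the same gap of 7 days (26 − 23 = 3 to 30 − 19 = 11). There is no later value.

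**3. Whether serum is available** (volume table, Section 7.2)

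- Serum to Beckman: 7 × 6 mL = 42 mL, which matches the table. Serum is therefore shipped from Visit 4 and End of Study as well.
- Whole blood to Quest: 7 × 4 mL = 28 mL, which also matches. Section 2.2 gives Quest one analyte, "hematocrit following injection measured by Quest Diagnostics", and that is listed at only four visits. The analyte lists and the volume table do not fit each other, so the lists may be incomplete.

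**4. How far a wrong SHBG could move free T (hypothetical)**

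The documents give no formula, albumin value or SHBG variability, so every input here is assumed: the mass-action quadratic with SHBG constant Ks = 1.0e9 L/mol, albumin constant Ka = 3.6e4 L/mol, albumin 4.3 g/dL at 69,000 g/mol, and testosterone at 288.4 g/mol.

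N = 1 + Ka × albumin = 1 + 3.6e4 × (43/69,000) = 23.43

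b = N + Ks × (SHBG − total T)

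free T = [−b + √(b² + 4 × N × Ks × total T)] / (2 × N × Ks)

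Example: total T 500 ng/dL = 17.34 nmol/L and SHBG 30 nmol/L. Then b = 23.43 + 30 − 17.34 = 36.10 and free T = (−36.10 + 54.11)/46.87 = 0.384 nmol/L. With SHBG 10% too high (33), free T is 0.364, a change of −5.3%. With SHBG 10% too low (27), it is 0.407, or +5.8%.

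Over total T 300, 500 and 800 ng/dL and SHBG 20, 30 and 40 nmol/L:

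| SHBG error | SHBG too high | SHBG too low |
|---|---|---|
| 5% | −1.9 to −3.2% | +1.9 to +3.4% |
| 10% | −3.7 to −6.2% | +3.8 to +6.9% |
| 20% | −7.1 to −11.7% | +7.9 to +14.8% |

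An albumin weight of 66,500 instead of 69,000 shifts these by at most 0.3 percentage points.

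**The case against.** The strongest reply is that this is a gap in a list and not in the measurements. A schedule that orders a calculated result can be read as ordering whatever the laboratory needs to produce it. SHBG at Visits 2, 3, 5 and 6 may simply be its own schedule as a secondary endpoint, and the serum volumes are compatible with running it at every visit. This stands in part: SHBG is not listed, which is not proof that it is unmeasured. But no section says it is run at Visit 4 or End of Study, and two separate lists leave it out.

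Second, the documents never say that free T is calculated from SHBG. That is correct. The link is a standard assumption, and the plan should confirm it or state another method.

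Third, the size of the harm is not established. The percentages above depend on assumed SHBG errors. Carrying forward the Day 7 and Day 21 values would treat the two periods alike, with each value from the same route as the sample it serves. Total T is intact at every visit. All of this stands: no bias between routes is shown, and duration of action can still be judged on total T. It does not repair the other primary endpoint at those times.

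Fourth, the missing formula and albumin handling leave free T undefined at all seven visits, which is a wider gap. True, but that is a separate matter and does not remove this one.

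**Conclusion.** The concern holds. As written, one primary endpoint lacks a same-visit SHBG at the last sample for each route: 2 of 6 post-injection values per man (33%), 40 of 120 in all. The 40 assumes 20 completers; dropouts after dosing, who are not replaced under Section 7.4, would lower it.

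The count comes directly from the two lists and is firm. That free T at those visits would be missing or less accurate rests on two assumptions: that the calculation uses SHBG, and that the laboratory runs only what is listed. The size of any error in free T cannot be established from the documents; the 2 to 15% range is illustrative. Sample size and power are not affected. It should be fixed before samples are analyzed, because the remedy is cheap and the affected times bear most on a stated hypothesis.

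**What to change.** - In footnote 5 and the Section 7.1 lists, add SHBG to the Beckman panel at Visit 4 and End of Study, and at Visit 1 if a free T baseline is wanted.
- In Section 2.1, state that free T is calculated from total T and SHBG of the same sample. Naming the formula and the albumin handling there would close the related gap.
- If the laboratory already runs SHBG on these samples, say so in footnote 5.

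Post-injection samples with a same-visit SHBG would rise from 80 to 120 of 120. The cost is 2 × 20 = 40 SHBG assays, or 3 × 20 = 60 with Visit 1, on the roughly 6 mL of serum already shipped from each visit, plus a short amendment. No extra blood or visit is needed. If SHBG is already run, the cost is the wording alone.
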